7.4.1. Study size

The study is not a hypothesis testing study, but it is designed to assess usage of CAB LA for PrEP in real world clinical settings. The overall number of participants in this cohort study will depend on the uptake of the CAB LA for PrEP and how widely it will be used across the NEAT-ID clinical sites.

The study aims to include a target of at least 500 participants initiating CAB LA for PrEP. There is no formal statistical hypothesis to be tested in these analyses. Table 1 below gives an indication of the likely precision of the estimates of the proportion with incident HIV, using Exact Clopper Pearson confidence limits under different scenarios.

Confidence Level	Sample Size (N)	CI Width	Incident HIV rate (%)	Lower Limit	Upper Limit
0.95	500	1.1824	0.25	0.0118	1.1942
0.95	500	1.5093	0.50	0.0832	1.5925
0.95	500	1.9926	1.00	0.3255	2.3181
0.95	500	2.3679	1.50	0.6283	2.9962
0.95	500	2.6841	2.00	0.9631	3.6472
0.95	500	2.9617	2.50	1.3185	4.2802
0.95	1000	0.7568	0.25	0.0416	0.7984
0.95	1000	1.0004	0.50	0.1625	1.1629
0.95	1000	1.3507	1.00	0.4806	1.8313
0.95	1000	1.6201	1.50	0.8419	2.4620
0.95	1000	1.8462	2.00	1.2258	3.0720
0.95	1000	2.0442	2.50	1.6243	3.6685
0.95	2000	0.5012	0.25	0.0812	0.5824
0.95	2000	0.6776	0.50	0.2400	0.9176
0.95	2000	0.9283	1.00	0.6119	1.5402

Table 1: Precision estimates

CONFIDENTIAL

CTMS Project Number: 221935 Final Protocol

				-	
0.95	2000	1.1202	1.50	1.0143	2.1345
0.95	2000	1.2810	2.00	1.4326	2.7136
0.95	2000	1.4217	2.50	1.8611	3.2828

Table 2 below shows the precision estimates for regimen discontinuation rates varying from 2.5% to 20% for a sample of 500 individuals.

Confidence Level	Sample Size (N)	CI Width	Discontinuation rate	Lower Limit	Upper Limit
0.95	500	0.0296	0.025	0.0132	0.0428
0.95	500	0.0403	0.050	0.0326	0.0729
0.95	500	0.0546	0.100	0.0751	0.1297
0.95	500	0.0646	0.150	0.1198	0.1844
0.95	500	0.0720	0.200	0.1658	0.2378

 Table 2. Precision estimates by discontinuation rate

7.5. Data management

Following the availability of CAB LA for PrEP in Europe, the study will collect followup data prospectively on a target of at least 500 individuals initiating CAB LA for PrEP, for a follow-up period of at least 3 years. Participants who discontinue CAB LA for PrEP will be followed up through the end of the follow-up period after discontinuation.

The NEAT-ID Network coordinating centre will receive data from the clinical sites per the protocol for the study. A detailed data collection form will be used to collect comprehensive data needed for study analysis, including clinical sites including dates of injections, clinical and laboratory parameters (immunologic, biochemistry, haematology and pathology), resistance and HIV subtype data at HIV acquisition, and after discontinuation and switching to another PrEP regimen.

In order to maintain confidentiality, the subject will be identified only by subject number. Subject data will be collected via extraction from individual medical record as source data by appropriately trained and authorised member(s) of the study team who must be identified and authorised in writing by the Principal Investigator (PI). A delegation of responsibility log will be updated accordingly.

Sites will provide and upload data to the data management team who will store the data on a secure database with access to authorised personnel of the study management team only, maintained the log of authorised personnel by the sponsor representative.

7.5.1. Data handling conventions

Data will be handled in accordance with data handling guidelines provided to sites. The Study Monitor and Data Manager will review data on an on-going basis and raise any discrepancies with site staff as required. Identified only by subject number, the data are deidentified at all times.

7.5.2. Timings of Assessment during follow-up

Available data will be collected from enrolled participants every 6 months, and deidentified data will be reported to the data coordinating centre.

7.6. Data analysis

7.6.1. Essential analysis

Specific analytic methods are shown for each study objective. All CAB LA PrEP users will be followed for at least 3 years (36 months). All individuals with incident HIV acquisition will be followed through the end of the follow-up period. Participants discontinuing CAB LA PrEP will be monitored through the end of the follow-up period for HIV acquisition and, in the case of HIV acquisition, will be monitored for ART effectiveness and potential emergence of resistance.

In the event of a delay of ART initiation post HIV diagnosis, the study team will strive to follow the individual through the end of the follow-up period. Interim results will be generated at 12, 24, 36, 48 months since study initiation and final results will be generated at 60 months since study initiation.

Analysis for Objective 1 (Description of CAB for PrEP Usage pattern)

For individuals initiating CAB for PrEP, baseline demographics (age, sex, gender, ethnic origin (where available), BMI, geographic region), history of previous PrEP use and use of OLI prior to initiating injections will be described. Comorbidities, STIs, risk factors for HIV acquisition (e.g. HIV status of sexual partner, multiple sexual partners), will be reported as frequencies at baseline and at 6, 12, 24, 36, and >36 months of follow-up as available. Proportion of individuals using oral PrEP to cover planned, delayed or missed CAB LA injections will also be provided. Frequency of testing for HIV once initiated CAB for PrEP will be evaluated, and timing of HIV testing relative to injection dates will be assessed.

Prevalent HIV is defined as any undiagnosed HIV at the time of PrEP initiation and will be defined as positive HIV antigen/antibody test and/or positive viral load from sample collected at the time of initiation (first prescription of CAB oral lead and, separately, first CAB LA PrEP injection). Note the test result may be reported within 4-6 weeks after the sample was collected. Prevalent HIV will be reported at baseline while on CAB OLI and while on CAB LA. Also, prevalent HIV will be reported for those who received CAB OLI and separately for those with direct to injection (DTI) strategy. Incident HIV is any new HIV diagnosis that occurs after the initiation of CAB PrEP, having confirmed HIV negative status using HIV RNA test, at the time of PrEP initiation. Incident HIV reporting is described in objective 3.

Analysis for Objective 2 (Monitor for adherence by assessing the frequency of delayed and missed injections without oral PrEP bridging)

Adherence will be estimated using the dates of injections. Proportion and number of individuals with ≥ 1 delayed (≥ 7 days)and/or ≥ 1 missed injection without oral PrEP bridging over 6, 12, 24, 36, >36-month periods will be provided. Additionally, mean (median) number of delayed and missed injections will be provided for each period. Proportion and number of individuals with ≥ 7 days delay of CAB LA PrEP injection over 6, 12, 24, 36, >36-month periods will be provided. Additionally, mean (median) number of days delayed will be provided for each period.

Characteristics of persons with delayed or missed injections without oral PrEP bridging will be compared with those that are on time with the injections for 6, 12, 24, 36, and >36-month periods using t-test for continuous variables (Wilcoxon rank sum test for not normally distributed variables) or chi-square test for categorical variables.

Proportion and number of individuals who discontinue CAB LA PrEP over 6, 12, 24, 36, and >36-month-periods and overall will be provided. Additionally, distribution of individuals who discontinued by most common discontinuation reasons will be provided and will be used to understand whether individuals are missing injections or choosing to discontinue the regimen. Characteristics of persons who discontinue vs persons who stay on therapy will be compared for 6, 12, 24, 36, and >36-month periods using t-test for continuous variables (Wilcoxon rank sum test for not normally distributed variables) or chi-square test for categorical variables.

If feasible, risk of delayed or missed injections and separately risk of discontinuation will be assessed using negative binomial model with log-link function accounting for sex, age group, race/ethnicity, and other characteristics found significant in univariate analysis.

Analysis for Objective 3 (Effectiveness: Monitor for incidence of HIV diagnoses while on CAB for PrEP)

Frequency of undiagnosed prevalent HIV at CAB PrEP initiation will be assessed as described for objective 1. The primary effectiveness measure for objective 3 is proportion of individuals with incident HIV diagnosis during OLI and separately during CAB LA PrEP and will be calculated at 6, 12, 24, 36 months and over the entire length of follow-up. The proportion of incident infections among those who start with OLI and those who go to DTI will also be reported separately along with the timing of diagnosis of incident HIV acquisition for the overall group, and separately for the OLI and DTI groups.

Adherence patterns and characteristics of individuals with incident HIV diagnosis will be compared with those without incident HIV diagnosis, using t-test for continuous variables (Wilcoxon rank sum test for not normally distributed variables) or chi-square test for categorical variables. Participant characteristics significantly impacting acquisition of HIV based on univariate analysis will be selected for multivariable analysis. Risk for HIV acquisition and characteristics affecting risk for HIV acquisition will be assessed using negative binomial model with log-link function with binary outcome (HIV diagnosis vs not) if feasible.

Time to HIV diagnosis will be defined as time from first CAB LA PrEP injection to the first HIV diagnosis using laboratory antigen/antibody test, confirmed by viral RNA test. Time to HIV diagnosis will be assessed using Kaplan-Meier curve. Differences in time to diagnosis will be assessed by sex, gender, ethnicity (where available), geographic region, and risk factors (e.g. STI, previous PrEP usage) related, adherence to current PrEP to HIV acquisition. Additionally, time to diagnosis will be shown for people who acquired the infection while prescribed oral CAB lead in (if applicable). Time to diagnosis in this group will be defined as time from first CAB oral prescription to the first positive HIV-1 antigen/antibody lab result, confirmed by viral RNA test.

If feasible, Cox proportional hazards models will be constructed to compare time to HIV diagnosis by subgroup adjusting for additional variables (e.g., sex, ethnicity, (where available) geographic region).

ART regimen and VL testing among CAB PrEP users with undiagnosed prevalent infections and incident infections will be described separately, during the follow-up period. In the event of a delay of ART initiation post HIV diagnosis, the study will strive to follow the individual after ART initiation and through the end of the follow-up period. Durability of INSTI-based vs. non-INSTI based regimens (e.g., the numbers and proportions of those who achieve and maintain virologic suppression, the time to virologic breakthrough), as well as any INSTI resistance-associated substitutions that are detected upon ART failure will also be assessed and reported.

Analysis for Objective 4 (Safety: Monitor for occurrence of DILI and HSR)

Proportion and number of individuals with DILI and HSRs following CAB OLI and CAB LA injections will be shown separately at 6, 12, 24, 36 months after initiation and over the entire length of the follow-up period. Proportion and number of individuals discontinuing CAB OLI and CAB LA PrEP due to DILI or HSR will be shown at 6, 12, 24, 36 months and over the entire length of the follow-up period. Discontinuation of CAB LA PrEP or CAB OLI will be based on medical records indicating date when discontinuation decision was made by a physician and will be reviewed and confirmed by an independent adjudication committee. Frequency of hepatotoxicity and HSR events will be reported separately for OLI period and during injections.

Analysis for Objective 5 (Resistance monitoring)

Proportion and number of individuals developing drug resistance to INSTIs based on genotypic data will be assessed among the 4 different groups as follows:

a) Individuals with undiagnosed prevalent HIV, initiating CAB OLI or CAB LA PrEP, will be followed through the end of the follow-up period after ART initiation and will be monitored for resistance

- b) Individuals with incident HIV while on CAB LA PrEP will be followed through the end of the follow-up period following ART initiation and monitored for resistance
- c) Individuals who discontinue CAB LA PrEP will be followed through the end of the follow-up period and if they acquire HIV will continue to be followed after ART initiation to monitor for resistance
- d) Individuals who switch to oral PrEP and acquire HIV during the 12- month follow-up period while on oral PrEP will be followed through the end of the follow-up period after ART initiation and monitored for resistance

Proportion and number of individuals developing specific mutations in each group will be provided along with HIV subtype. Description of the methodologies used to evaluate resistance will be described.

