6. RESEARCH QUESTION AND OBJECTIVE(S)

The study will aim to assess usage patterns, adherence, effectiveness, safety, and resistance among individuals initiating CAB LA for PrEP.

The specific objectives are to assess:

- 1) CAB LA for PrEP usage pattern:
 - a. Describe the population initiating CAB LA for PrEP by:
 - i. Baseline demographics (age, sex, gender, ethnic origin, geographic region, BMI)
 - ii. Risk factors for HIV acquisition: STI diagnoses, substance use including injection drug use
 - iii. PrEP: History of previous PrEP use
 - iv. OLI or DTI: proportion of individuals who use OLI prior to initiating injections and proportion of individuals DTI

- b. Describe the individuals initiating CAB OLI or CAB LA PrEP with undiagnosed HIV acquisitions by baseline demographics and PrEP history
- c. Describe oral PrEP used to cover planned, delayed or missed CAB LA injections
- d. Assessing the frequency of testing for HIV and methods used for HIV-1 diagnosis, as well as assessing the timing of HIV testing relative to CAB LA for PrEP initiation injections and maintenance injections

Undiagnosed (prevalent) HIV acquisitions will be defined as positive laboratory HIV antigen/antibody test or positive viral load (RNA assay) following first prescription of CAB OLI and separately, following first CAB LA for PrEP injection. The date of the assay should be at the time of the first prescription or injection while the result may be reported within 4-6 weeks after first prescription or injection. Prevalent HIV will be shown for those who received CAB OLI and those who used DTI strategy.

- 2) Treatment adherence (Medication errors): Monitor for adherence by assessing the frequency of delayed and missed injections without oral PrEP bridging
 - a. Delayed and missed injections (non-adherence to the scheduled dosing)
 - i. Determine the number of individuals that miss one or more consecutive injections without daily oral PrEP bridging
 - ii. Assess the mean and median number of injections missed during the 6-month and 12-month period without oral PrEP bridging
 - iii. Determine the number of individuals who receive the injections seven or more days later than their scheduled injection visit and median duration of delay
 - iv. Describe characteristics of the individuals that are non-adherent
 - b. Discontinuation of CAB LA PrEP
 - i. Determine the proportion of individuals who discontinue CAB LA PrEP after 6, 12, 24, 36, and >36 months

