7.4. Data sources

Data will be collected from participating European clinical sites within the NEAT-ID Network. Selected sites will be contacted and asked to identify individuals initiating CAB LA for PrEP. The NEAT-ID Network coordinating center will receive data from the clinical sites for the study; data will be extracted from medical records to capture the study variables relevant to the study objectives, as listed in Section 7.3 Variables. Data will be entered into the EDC system from each site. All data will be deidentified and electronically transferred to the coordinating center. Sites will be regularly monitored for data quality and accuracy.

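### Objective 2 compares late, missed and discontinued users with tests that ignore clinic, so p-values for geographic region, and less so for oral lead-in versus direct to injection, can be too small, and Table 2 is optimistic beyond the enrolled clinics

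*Protocol*

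**What the plan says.** Protocol section 7.6.1 opens by saying that the analytic methods are given objective by objective, and for Objective 2 it names them. For adherence, "Characteristics of persons with delayed or missed injections without oral PrEP bridging will be compared with those that are on time with the injections" at each of five periods, by t-test, Wilcoxon rank sum or chi-square. For discontinuation, "Characteristics of persons who discontinue vs persons who stay on therapy will be compared for 6, 12, 24, 36, and >36-month periods using t-test" and the same alternatives. If feasible, the risk of delay or missed injection and the risk of discontinuation are then modelled with a "negative binomial model with log-link function accounting for sex, age group, race/ethnicity, and other characteristics found significant in univariate analysis".

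The data come from clinics. Section 7.4 says "Data will be collected from participating European clinical sites within the NEAT-ID Network" and "Selected sites will be contacted and asked to identify individuals initiating CAB LA for PrEP". Section 7.2.1 has clinics chosen through a feasibility questionnaire, and section 7.8 says the study reflects treatment practice across the network's clinics. Up to six countries are listed as potential.

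The characteristics to be described include "Baseline demographics (age, sex, gender, ethnic origin, geographic region, BMI" and use of oral lead-in (OLI) or direct to injection (DTI). Section 7.3.3 repeats geographic region, where provided, and OLI use.

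On precision, section 7.4.1 says "Table 2 below shows the precision estimates for regimen discontinuation rates varying from 2.5% to 20% for a sample of 500 individuals". The same section states that no formal hypothesis is tested. The protocol gives no number of clinics, clinic size or ICC. Nowhere does it mention a site term, stratification by site, a random effect or a clustered variance.

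**The concern.** The t-test, Wilcoxon and chi-square tests treat the participants as independent. Whether an injection is late, bridged or abandoned may depend partly on the clinic, since appointments and injections are handled there. If so, people at one clinic resemble each other. A characteristic that is the same for everyone at a clinic is then tested with too small a variance.

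Geographic region is such a characteristic, taking it to be the region of the clinic. OLI versus DTI is partly of this kind if clinics have a habitual starting strategy. For these, ordinary differences between clinics could be reported as an effect of region or starting strategy. They could also enter the multivariable model through the significance screen.

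Adherence and durability is among the primary outcomes in the synopsis. Objective 2 asks who is non-adherent and who discontinues, so these comparisons are the study's answer to that question. Table 2 is the only stated precision for discontinuation, and it too treats 500 people as independent.

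**Working it through.** **Inputs from the protocol.** N = 500, discontinuation rates of 2.5% to 20%, 95% limits (section 7.4.1); up to six countries (study information); the tests named in section 7.6.1.

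**Assumptions, because the protocol is silent.** 10, 20 or 50 clinics of equal size; ICC 0.01 to 0.10; two-sided 5% level; six region levels with clinics nested in them and no true region effect.

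**Step 1: reproduce Table 2.** Exact Clopper-Pearson limits with x = 500p and n = 500 give 0.0132–0.0428, 0.0326–0.0729, 0.0751–0.1297, 0.1198–0.1844 and 0.1658–0.2378. All five rows match the printed limits. The table contains no arithmetic error and is an independent-binomial calculation.

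**Step 2: design effect.** DEFF = 1 + (m − 1) × ICC, where m is participants per clinic. With 20 clinics, m = 500/20 = 25. At ICC 0.05, DEFF = 1 + 24 × 0.05 = 2.20, and the effective sample size is 500/2.20 = 227.

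**Step 3: false positives for region.** A six-level chi-square has 5 degrees of freedom and a 5% critical value of 11.07. If the statistic is inflated by DEFF, the true rejection probability is P(χ²₅ > 11.07/2.20 = 5.03) = 0.41. A beta-binomial simulation (4,000 runs, 20% discontinuation) gives the same 41%. Simulated rates across the assumed range:

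| Clinics | ICC 0.01 | ICC 0.02 | ICC 0.05 | ICC 0.10 |
|---|---|---|---|---|
| 10 | 18% | 35% | 67% | 88% |
| 20 | 11% | 18% | 41% | 66% |
| 50 | 7% | 9% | 18% | 32% |

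**Step 4: other characteristics.** A person-level characteristic balanced across clinics was rejected 4% to 6% of the time in every setting. A person-level characteristic that itself clusters by clinic (ICC 0.10) gave 5% to 8% with 20 or 50 clinics and up to 10.6% with 10. For OLI versus DTI, assuming 50% mean use and a between-clinic ICC of OLI use of 0.3, the chi-square rejected 8% to 10% of the time at 20 clinics and outcome ICC 0.05.

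**Step 5: do site-aware tests repair it?** At 20 clinics and ICC 0.05, site-level tests for country and a Cochran-Mantel-Haenszel test by site for OLI/DTI rejected 4.6% to 5.5% of the time.

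**Step 6: Table 2 with clustering.** Clopper-Pearson limits at the effective sample size, 20 clinics:

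| ICC | DEFF | Effective n | Width, 10% row | Width, 20% row |
|---|---|---|---|---|
| 0 (as printed) | 1.00 | 500 | 0.0546 | 0.0720 |
| 0.01 | 1.24 | 403 | 0.0610 | 0.0804 |
| 0.02 | 1.48 | 338 | 0.0669 | 0.0880 |
| 0.05 | 2.20 | 227 | 0.0823 | 0.1080 |
| 0.10 | 3.40 | 147 | 0.1036 | 0.1352 |

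Over all settings, the 20% row runs from 0.0752 (50 clinics, ICC 0.01) to 0.180 (10 clinics, ICC 0.10). Recruiting more people at the same clinics helps little: 1,000 people in 20 clinics at ICC 0.05 give DEFF = 1 + 49 × 0.05 = 3.45 and an effective n of 1,000/3.45 = 290.

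**The case against.** **This is detail for the statistical analysis plan.** Variance methods and random effects are often left there, the model is conditional on feasibility, and its covariate list is open. That is fair for the model: nothing in the protocol excludes a site term, and the model itself was not simulated. It does not cover the univariate tests, which the protocol names outright.

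**The study is descriptive.** No formal hypothesis and no significance level are stated, and Objective 2 asks for a description of characteristics. This limits the consequence to exploratory p-values. It does not remove it, because "accounting for sex, age group, race/ethnicity, and other characteristics found significant in univariate analysis" makes univariate significance the entry rule for the model.

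**The size is assumed.** This stands. With many clinics and an ICC near 0.01 the excess is negligible. A reader might infer that clinic- and region-level predictors will be declared far too often. The documents do not support that as a fact: they give neither quantity, they list no clinic-level characteristic, and region is the only clearly group-level one.

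**Table 2 is not wrong.** This also stands. A reader might infer an error in the table, or that reported 95% intervals for delay and discontinuation will undercover. The table reproduces exactly, and section 7.6.1 promises numbers and proportions for these outcomes, not intervals. The target also matters. At 20 clinics and ICC 0.05, the exact interval covers 96% to 97% for the rate in the enrolled clinics and 82% to 84% for the rate in a wider population of similar clinics. The protocol does not say which is meant, and its clinics are selected by feasibility, not sampled at random.

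**Conclusion.** The point holds in a conditional form. The protocol names tests that assume independent participants and uses their significance to choose model covariates, although participants are grouped in clinics. If delay or discontinuation varies between clinics, p-values for region can be too small. Those for OLI versus DTI can be too small by a lesser amount if its use follows clinic practice.

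The direction is clear for any positive ICC; the size is not known. At nominal 5%, the region test errs about 7% of the time with 40 to 50 clinics and ICC 0.01, about 41% with 20 clinics and ICC 0.05, and more with fewer clinics or a larger ICC. Person-level characteristics balanced across clinics are unaffected. All figures assume equal clinic sizes; unequal enrolment would generally raise the design effect.

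Table 2 is correct for what it computes. Its limits may be too narrow only for inference beyond the enrolled clinics. This is a worthwhile, inexpensive improvement to exploratory analyses, not a flaw in a confirmatory conclusion.

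**What to change.** In section 7.6.1, Objective 2:

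- For person-level characteristics, including OLI/DTI, use site-stratified tests (Cochran-Mantel-Haenszel, van Elteren) or regression with site-clustered standard errors.
- For geographic region, compare at site level, or use a model with a random site effect and a small-sample correction.
- Fit the multivariable delay and discontinuation models with a site random effect or site-clustered standard errors.
- If intervals for delay or discontinuation proportions are reported beyond the enrolled clinics, make them cluster-adjusted.

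In section 7.4.1, note under Table 2 that it assumes no clustering by site, and show the limits for a range of design effects, for example 1.2 to 3.4.

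The cost is wording and standard software. No new data or participants are needed, since data arrive site by site and the site of each participant should be known to the coordinating centre. The price is wider intervals, fewer nominally significant characteristics, and low power for region when clinics are few.

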7.3.3. Confounders and effect modifiers

The study will examine the effect of the following potential confounders and effect modifiers on the risk for outcomes of interest. These variables will be measured at baseline and at 6, 12, 24, 36, and >36 months as available.

Demographic Variables

- Age at index date
- Sex and Gender
- Ethnic Origin
- Geographic region (where provided)

Clinical Characteristics

- Substance use
- Alcohol use
- Charlson Comorbidity Index (CCI)
- Body Mass Index (BMI), weight, height
- High risk sexual behaviour
- STI testing in the past 12 months
- STI diagnoses in the past 12 months (chlamydia, syphilis, gonorrhoea, and other STIs combined)
- Cardiovascular
 - Hypertension as >130 mmHg systolic, >=90 mmHg diastolic,
 - \circ Triglycerides >=1.5 g/l
 - LDL > 100 mg/dL, Index of Total Cholesterol/HDL Cholesterol
 - ASCVD risk >7.5%
 - CVD incidence
- Hepatic: the following liver chemistry tests (LCT) data will be collected when tested for:
 - Alanine aminotransferase (ALT) elevations (also called serum glutamic pyruvic transaminase (SGPT))
 - Aspartate aminotransferase (AST) elevations (also called serum glutamic oxaloacetic transaminase (SGOT))
 - Total bilirubin elevations (BILI)
 - Alkaline phosphatase (ALP) elevations where available
 - o Albumin
 - Prothrombin time (PT) where available
 - Lipase levels where available
 - o Fib-4
- Hepatitis C and hepatitis B incidence and chronic infection
- Use of recreational drugs (cocaine, narcotics, psychodysleptics [hallucinogens], psychoactive substance, antiepileptic, sedativehypnotic and anti-parkinsonism drugs)

History of PrEP use

- Current or any prior daily PrEP use (yes, no)Time and duration on prior daily PrEP use:<2 months
 - \circ 2-6 months
 - \circ 6-12 months
 - \circ 12+ months
- Number of months on PrEP in the last 12 months (mean and median)
- Type of daily PrEP used (TDF, TAF)
- Use of CAB oral lead in prior to initiating injections

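### Section 7.6.1 chooses covariates for the two Objective 2 models by univariate significance, on the same data that then estimate their effects

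*Protocol*

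**What the plan says.** The Objective 2 part of Section 7.6.1 of the protocol works in two steps.

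- **Univariate comparisons.** Participants with delayed or missed injections are "compared with those that are on time with the injections for 6, 12, 24, 36, and >36-month periods using t-test for continuous variables", with rank-sum or chi-square tests where a t-test does not suit. A parallel comparison covers stopping: "Characteristics of persons who discontinue vs persons who stay on therapy will be compared for 6, 12, 24, 36, and >36-month periods".
- **Models.** Each of the two outcomes then gets a conditional model: "If feasible, risk of delayed or missed injections and separately risk of discontinuation will be assessed using negative binomial model with log-link function". The adjustment set for both is fixed by a rule in the same sentence, namely "accounting for sex, age group, race/ethnicity, and other characteristics found significant in univariate analysis". Three covariates are thus forced in, and the rest enter on significance.

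The text gives no test level, no list of candidate characteristics and no period for the screen or the model.

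Three other places bear on this. Section 7.3.3 lists covariates for the study as a whole: "The study will examine the effect of the following potential confounders and effect modifiers on the risk for outcomes of interest". Section 7.4.1 says "There is no formal statistical hypothesis to be tested in these analyses". Section 7.6.1 also says "Interim results will be generated at 12, 24, 36, 48 months since study initiation", with final results at 60 months.

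**The concern.** A covariate that enters because it was significant in these data carries its chance component into the model. Its adjusted estimate and interval ignore the filter it passed, so a chance predictor can look confirmed. A weak real factor is either dropped or reported too large.

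This is a method that the protocol states, not a detail left to a later analysis plan: a plan that follows the protocol has to apply it. It also fits poorly with Section 7.4.1, because significance tests decide what is modelled in a study said to test no hypothesis. Who misses injections and who stops is a stated objective, and the results go to the regulator, so characteristics wrongly singled out would matter.

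**Working it through.** **1. The plan's own related figure.** The protocol gives no error rate for the screen. The nearest figure is Table 2, the exact 95% limits for discontinuation at n = 500. With x = np, the Clopper-Pearson limits are the 0.025 quantile of Beta(x, n − x + 1) and the 0.975 quantile of Beta(x + 1, n − x). They give 0.0132 to 0.0428 at 2.5% and 0.1658 to 0.2378 at 20%. All Table 2 limits reproduce to four decimals. The implied numbers of discontinuers run from 0.025 × 500 = 12.5 (about 12) to 0.20 × 500 = 100.

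**2. Number of candidates (assumption).** Section 7.3.3 has 32 items as listed, or 34 if sex is split from gender and hepatitis B from hepatitis C. Sex, age group and ethnicity are forced in, so at most 34 − 3 = 31 are screened. Ten is used as a short-list alternative.

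**3. One screen, one outcome, all candidates null, two-sided 0.05 (assumed).** Expected chance selections = 0.05m. If candidates are independent, P(at least one) = 1 − 0.95^m.

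| Candidates m | Expected | P(at least one), independent | With correlation 0.5 (simulated) |
|---|---|---|---|
| 10 | 0.5 | 0.40 | 0.29 |
| 31 | 1.55 | 0.80 | not tabulated |
| 34 | 1.7 | 0.83 | 0.53 |

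**4. What happens after the screen.** Simulation with n = 500, three forced covariates, 31 independent null candidates, a t-test screen at 0.05, then a log-link refit. Coverage is that of nominal 95% intervals for the null covariates that were selected.

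| Outcome and standard errors | Coverage | Studies with at least one null covariate significant in the final model |
|---|---|---|
| Binary, 10% to 40% events, Poisson fit, robust | 10% to 16% | 75% to 80% |
| Binary, 10% to 40% events, Poisson fit, model-based | 32% to 78% | 29% to 66% |
| Count, negative binomial fit | 52% to 56% | 50% to 54% |

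The model-based Poisson errors are too wide for a binary outcome, which is why they look better. With a covariate list fixed in advance and robust errors, coverage was 93.5% to 94.3% for 10 covariates and 93.8% for 34.

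**5. Real effects.** Same set-up, but with 5 candidates, 20% events and robust errors; results are for the real covariate when selected.

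| True log risk ratio | Mean estimate when selected | Coverage when selected |
|---|---|---|
| 0.10 | 0.22 | 85% |
| 0.20 | 0.25 | 96% |
| 0.30 | 0.32 | 97% |

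The weak effect roughly doubles on the log scale. At 0.20 to 0.30 coverage is not harmed and the remaining inflation is small.

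**The case against.** The strongest reply is that these models are secondary and descriptive. They are run only if feasible, no formal hypothesis is tested, Section 7.8 asks for cautious interpretation, and the main Objective 2 outputs do not depend on them. That stands, and it limits the consequence. It does not justify the rule, because significance still decides which characteristics receive an adjusted estimate.

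A second reply is that low coverage for selected nulls partly restates the selection rule: a null kept because p < 0.05 will tend to have an interval that excludes the null. This is fair, and the figure depends heavily on the model used. It is still what a reader of the fitted model would face, and the inflation of weak real effects is a separate cost.

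A third is that candidate lists, main periods and multiplicity statements are usual analysis-plan content. That also stands, and their absence here is not the point. The point is the selection clause that the protocol does state.

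A reader might go further and count 34 characteristics × 5 periods × 2 outcomes = 340 tests, with 0.05 × 340 = 17 false positives expected, repeated at each interim report. The documents do not require that. Section 7.6.1 does not tie the screen to Section 7.3.3, a list that also serves the liver outcomes and includes items such as lipase and prothrombin time. It does not say that a result in any one period admits a covariate, or that the models are refitted at each interim. Three of the 34 are forced in anyway. The count is an upper scenario.

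A reader might also infer that invalid confidence intervals will be reported. The protocol promises no intervals for these models, so that is conditional on the models being run and reported in the usual way.

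**Conclusion.** The point holds in limited form. The protocol fixes selection by univariate significance for both Objective 2 models, with selection and estimation on the same data. On the one-screen reading with 31 independent null candidates at 0.05, about 1.6 chance entries are expected per outcome and the chance of at least one is about 80%. It falls to 29% to 40% with 10 candidates, and to 53% with 34 candidates correlated at 0.5. If the models are run, intervals for selected null covariates cover well below 95% in every setting tried, and weak real effects are overstated when selected.

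These sizes rest on the assumed 0.05 level, the assumed candidate list and simulated data. Interval coverage for moderate true effects, the Objective 2 proportions and Table 2 are not affected. It would be wrong to assume that events are plentiful enough for a long covariate list: the lower end of Table 2 is about 12 discontinuers in 500. The change is worth making before the first interim report applies the rule.

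**What to change.** In the Objective 2 part of Section 7.6.1:

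1. Delete the clause that admits further characteristics on univariate significance.
2. Name a short covariate set in advance from baseline variables already collected, for example sex, age group, ethnic origin where available, prior PrEP use, and oral lead-in versus direct to injection. Keep each whatever its p-value. State that the set will be reduced if events are few, since Table 2 implies about 12 to 100 discontinuers in 500 and several of these variables have more than two levels.
3. State that the by-period comparisons are exploratory and do not select covariates.

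The cost is wording in the protocol and in any analysis plan, with no new data or participants. The downside is that a factor outside the list appears only in the descriptive tables.
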